Effect of Individualized Repetitive Transcranial Magnetic Stimulation (rTMS) in Patients With Disorder of Consciousness

	Effect of Individualized Repetitive Transcranial Magnetic Stimulation (rTMS) in Patients With Disorder of Consciousness							
Application	Department of Rehabilitation, Zhujiang Hospital, Southern Medical University							
	Primary objectives: To examine whether individualized rTMS is more effective to improve CRS-R scores in DoC patients than the rTMS-sham control.							
	Secondary objective: (1)To examine whether individualized rTMS is more effective to improve relative spectral power of EEG in DoC patients than the rTMS-sham control;							
	(2)To examine whether individualized rTMS is more effective to improve functional connectivity of EEG in DoC patients than the rTMS-sham control;							
	(3)To evaluate the safety of rTMS in DoC patients.							
	rTMS applied on the Individual-targeted selection area will improve DOC patients' level of consciousness							
Design	Exploratory single-center, cross-over, double-blind, randomized controlled trial							
	This is a crossover pilot study. The CRS-R total score after two-stage treatments will be considered as the primary efficacy outcome, while high-density EEG analysis (relative spectral power and functional connectivity) will be the secondary outcome. In this context ^[1] , the sample size calculation will be based on an expected difference between the treatment groups of 20%, setting a significance level of 0.05% and a power of 80%. Considering patients' compliance and approximately 20% dropout rate during the study, the final sample size of 30 participants is needed. We consider this is an achievable sample size and adequate to allow for the dropout rate while still leaving a reasonable final sample.							
Eligibility	Inclusion Criteria:							
	1) acquired brain injuries less than 1 year and more than 28 days in DOC;							
	2) no medical history of neuropsychiatric diseases;							
	3) no contraindications for rTMS or EEG, no sedatives in use or other drugs that might interfere with brain stimulation, such as Na+ or Ca2+ channel blockers or NMDA receptor antagonists;							
-	4) stable state of disease and vital signs;							
	5) the families of the patients volunteered the patient to participate in the study and provided signed informed consent;							
	6) the integrity of the individualized stimulation target cortex are verified by MRI.Exclusion criteria:							

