-	Exclusion Criteria:							

	1) patients in other non-invasive or invasive neuroregulation trials;							
	2) motor evoked potential (MEP) in M1 region cannot be induced by TMS pulse;							
	3) uncontrolled epilepsy, seizure within 4 weeks before enrollment;							
	4) metallic implant in the skull, pacemaker, craniotomy under the stimulated site, implanted brain device.							
Major interventions	10Hz rTMS							
Evaluating indicator	Primary outcome: The Coma Recovery Scale-Revised (CRS-R), a total of 23 points, is widely used to define the level of consciousness and assess neurobehavioral recovery of patients with DOC. It is based on six subscales that assess auditory (4 points), visual (5 points), motor (6 points), motor/speech (3 points), communication (2 points), and arousal processes (3 points). Each item of CRS-R is in good agreement with the diagnostic and differential diagnostic criteria of VS/UWS, MCS and EMCS. The higher scores mean a better outcome.							
	Secondary outcome: EEG will be acquired from 66 channels with positions of the International 10-20 System for 10 mins. The relative spectral power (RSP) and functional connectivity (FC) of participants will be calculated by the selected artifact-free EEG epochs at five frequency bands: δ (1-4 Hz), θ (4-8 Hz), α (8-13 Hz), β (13-30 Hz), and γ (30-45 Hz). The investigators will compute off-line analysis to calculate RSP and FC.							
Statistical method	Statistical hypothesis: Parametric hypothesis test							
	1. Group mean CRS-R scores before and after active/sham rTMS were analyzed by ANOVA with a two-stage crossover design;							
	2. The relative spectrum power and coherence before and after active/sham rTMS were analyzed by ANOVA with a two-stage crossover design;							
	3. If the overall means were unequal across each group, pairwise comparisons were performed using the SNK-q test;							
	4. Select the channel of interest at the average level of the active/sham rTMS group, extract the relative spectrum energies of each frequency band, and use the paired-sample t-test to compare the differences between the relative spectrum energies of the two groups;							
	5. Pairwise channel coherence was calculated along each channel at the mean frequency band of active/sham rTMS group using the paired sample t-test to compare the differences between the specific channel coherence of the two component pairs;							

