	Non-parametric test was used if the normal distribution is not satisfied.							
	Effectiveness test: The efficiency test adopts the 2 test of paired R x C contingency table data. If the sample size is <40 or T <1, the Fisher exact probability method of four table data is used;							

#Table 1 Schematic timeline of the study

TIMEPOINT	Enrollment	Allocation	Post-allocation					Close-out
	- t ₁	t_0	t_1	t_2	t ₃	t 4	t ₅	t ₆
Enrolment	×							
Eligibility screen	×							
Informed consent	×							
Demographic information ¹⁾	×							
Medical history ²⁾	×							
Vital signs ³⁾	×			×		×		
Randomization		×						
Allocation		×						
Interventions								
Active rTMS			×		Washout	\rightarrow	×	
Sham rTMS			×		Washout	\rightarrow	×	
Assessments								
CRS-R ⁴⁾	×			×		×		×
EEG recording ⁵⁾	×			×		×		×
Adverse events			×	×	×	×	×	×

- 1) Demographic information includes the patients date of birth, sex and race;
- 2) Medical history includes DoC resulting from brain injury and other clinically significant past and present medical history;
- 3) Vital signs include blood pressure, pulse rate, respiration and body temperature;
- 4) CRS-R: Coma Recovery Scale-Revised;
- 5) EEG: Electroencephalogram.

Reference:

[1] Steven-A Julious. Sample size of 12 per group rule of thumb for a pilot study[J]. Pharmaceutical Statistics, 2005, 4(4): 287-291.

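### The categorical effectiveness test is written for paired data, but its below-40 rule sends this 30-patient crossover to a fourfold Fisher test, so the paired test is never used

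*Protocol*

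**What the plan says.** The protocol describes the trial as "Exploratory single-center, cross-over, double-blind, randomized controlled trial", so each patient is planned to receive both active and sham stimulation.

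Under Statistical method, the effectiveness test reads: "The efficiency test adopts the 2 test of paired R x C contingency table data". (The chi symbol was probably lost when the text was extracted.) The sentence after it sets a switching rule: "If the sample size is <40 or T <1, the Fisher exact probability method of four table data is used". T is not defined; by convention it is the smallest expected cell count. The fallback no longer mentions pairing.

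The Design section fixes the number to which the rule applies: "approximately 20% dropout rate during the study, the final sample size of 30 participants is needed".

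The primary outcome does not pass through this rule. Item 1 of Statistical method states: "Group mean CRS-R scores before and after active/sham rTMS were analyzed by ANOVA with a two-stage crossover design". EEG power and coherence have crossover ANOVA and paired t-tests.

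**The concern.** The two conditions of the switching rule are joined by *or*, so a sample size below 40 is enough to trigger it. At the planned size the paired test that the protocol names first cannot be reached, and nothing else in the protocol keeps a paired categorical method for small samples.

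A rule of this kind belongs to independent fourfold tables, and the data here are pairs. The rows and columns of the fourfold table are not stated, and two layouts follow naturally from a sentence about paired data:

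- **Active response by sham response, one count per patient.** Fisher then tests whether a patient who responds in one period also tends to respond in the other. That is not the treatment effect. The test can be significant when the two response rates are identical, and can miss a real difference.
- **Treatment by response, with active and sham results stacked.** Fisher does compare active with sham, but counts each patient twice as if the results were independent. With positive within-patient correlation this is conservative and gives up the advantage of the crossover.

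A fourfold test also does not fit an R x C table with more than two categories unless the categories are collapsed, and no collapsing is described.

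At stake is a p-value that the protocol labels as a test of effectiveness and that a reader could take as evidence of benefit.

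**Working it through.** **Inputs from the protocol.** 30 participants; about 20% dropout; crossover; switch to Fisher below 40.

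**Inputs assumed.** The protocol gives no response rates and no within-patient correlation, so both are varied below. Tests are two-sided at 5%.

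**Step 1: the plan's own number and the trigger.** The cited pilot rule of 12 per group gives 2 × 12 = 24, and 24 / (1 − 0.20) = 30, which reproduces the stated size. Completers: 30 × 0.80 = 24. Both 30 < 40 and 24 < 40 hold, so Fisher applies whatever T is.

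**Step 2: two worked tables, 24 patients each.** Cells are both respond / active only / sham only / neither.

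*Table A: 7 / 1 / 1 / 15.* Response is 8/24 on active and 8/24 on sham, so there is no difference.
- Exact McNemar, 1 against 1 discordant: p = 1.0.
- Fisher on the paired table: [C(8,7)·C(16,1) + C(8,8)·C(16,0)] / C(24,8) = (128 + 1) / 735,471 = 0.0002.

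*Table B: 3 / 9 / 1 / 11.* Response is 12/24 on active and 4/24 on sham.
- Exact McNemar, 9 against 1: 2 × (1 + 10) / 2^10 = 22/1024 = 0.021.
- Fisher on the paired table: p = 0.59.
- Fisher on stacked margins, 12/24 against 4/24: p = 0.030.

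**Step 3: rejection rates.** All possible paired 2 × 2 tables were enumerated exactly. With response probabilities p1 (active) and p2 (sham) and correlation ρ, the probability that a patient responds to both is

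p11 = p1·p2 + ρ·√[p1(1 − p1)·p2(1 − p2)],

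and the other cells follow by subtraction. For example, at 30%/30% and ρ = 0.5, p11 = 0.09 + 0.5 × 0.21 = 0.195, and each discordant cell is 0.30 − 0.195 = 0.105.

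No treatment effect, 30% on both, n = 24:

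| ρ | Fisher, paired table | Fisher, stacked |
|---|---|---|
| 0 | 2% | 2.6% |
| 0.2 | 11% | 1.3% |
| 0.3 | 23% | 0.8% |
| 0.5 | 59% | 0.2% |

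Exact McNemar stays at or below 2.3% throughout. At ρ = 0.76, paired-table Fisher rejects 95%.

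Real effect, 50% active against 20% sham, n = 24:

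| ρ | Fisher, paired table | Fisher, stacked | Exact McNemar |
|---|---|---|---|
| 0 | 2% | 49% | 46% |
| 0.2 | 8% | 49% | 55% |
| 0.3 | 17% | 49% | 61% |
| 0.5 | 58% | 48% | 77% |

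Here ρ = 0.5 is the largest value possible: p11 = 0.10 + 0.5 × 0.20 = 0.20, which equals the whole sham response rate and leaves the sham-only cell at zero. The last row is therefore an upper limit.

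The first columns of the two tables are nearly the same: paired-table Fisher responds to the correlation and hardly at all to the treatment effect.

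**Step 4: sensitivity.**
- n = 30, no effect at 30%: paired-table Fisher rejects 3%, 15%, 31% and 72% at ρ = 0, 0.2, 0.3 and 0.5.
- n = 30, 50% against 20%: stacked Fisher has 60%, 61% and 63% power at ρ = 0, 0.2 and 0.5; exact McNemar has 59%, 68% and 92%.
- n = 24, no effect, 20% or 40% response on both: paired-table Fisher rejects 11% and 11% at ρ = 0.2, and 52% and 61% at ρ = 0.5.

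**The case against.** **Sample size could mean observations.** Stacked, there would be 60 results, or 48 after dropout, and the below-40 condition would not be met. But the Design section counts participants, and the size of a paired table is its number of pairs. This reading goes against the protocol's own usage.

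**Some fourfold Fisher tests are valid in a crossover.** One sets sequence against period of better response among discordant patients; another compares the two sequences in the first period only. The protocol excludes neither, and table layout could be left to an analysis plan that is not shown. However, neither is what a sentence about paired R x C data describes, and the switching rule is a stated choice, not an omission.

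**The stacked reading does little harm.** This largely stands. Type I error is below 5%, and the power of stacked Fisher stays about flat as the correlation rises; the loss is only relative to what McNemar would achieve. At ρ = 0 and n = 24, stacked Fisher is slightly ahead, 49% against 46%. In Table B it reaches the same conclusion as McNemar.

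**The large error rates need the less favourable layout and a sizeable assumed correlation.** True, and the protocol gives no figures to settle either. But it does not rule out that layout, which is the usual way to display paired data.

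**The reach is small.** This stands: no categorical outcome is listed among the objectives or evaluating indicators.

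**McNemar ignores period.** This also stands in part. Patients are between 28 days and 1 year from injury, so change over time is plausible, and unequal sequences after dropout would mix period with treatment. It is a reason to add a period-adjusted analysis, not to keep the present rule.

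**Conclusion.** The concern holds. With sample size read as participants, as the protocol uses it, the switch to Fisher is certain at 30 or 24 patients and the paired test named first is never used.

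The consequence depends on the undefined table. On the active-by-sham layout the test does not address the treatment effect: at n = 24 and an assumed 30% response on both, it rejects between 2% and 59% of the time for correlations from 0 to 0.5. On the stacked layout the test is conservative, and for an assumed 50% against 20% it gives up from nothing at correlation 0 to 29 points of power (77% − 48%) at 0.5. Response rates and correlations are assumptions, so these figures show direction and order of size only.

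The point should be fixed, but it is confined to the supplementary categorical test. The CRS-R and EEG conclusions do not depend on it.

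**What to change.** Replace the switching rule with a sentence such as:

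> For a binary response, active and sham will be compared by the exact McNemar (binomial) test on discordant patients, at any sample size.

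If more than two categories are kept, name an exact Stuart-Maxwell (marginal homogeneity) test instead. The Mainland-Gart test, which applies Fisher validly to sequence by period of better response among discordant patients, can be added as a period-adjusted sensitivity analysis.

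The cost is one sentence in the statistical section. No new data, visits or patients are needed.
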